To our knowledge, the efficacy of breath-enhanced compared to t-piece nebulizers on airway obstruction as determined by spirometry has not been evaluated in children with acute asthma. There is an ongoing study at our institution (principal investigator is [name]) that is evaluating ED LOS in pediatric asthma patients when placed on a breath-enhanced versus t-piece nebulizer treatment pathway. [name] study is not evaluating FEV₁ or other spirometric data to measure airway obstruction or the efficacy of a single treatment. Measurement of FEV₁ has been used throughout other asthma literature as a reliable measure of airway obstruction and effectiveness of treatment in patients with acute asthma.¹⁶⁻¹⁹ FEV₁ measurement has been recommended by the National Heart, Lung, and Blood Institute (NHLBI) as a means of assessing the degree of airway obstruction, and response to therapy in acute asthma.² In their 2007 guidelines, the NHLBI recommended routine FEV₁ measurements in all patients presenting for acute asthma exacerbations, as this measure is a more reliable indicator of severity of exacerbations than severity of symptoms.² Additionally, FEV₁ is more useful than peak expiratory flow (PEF) due to the ability to evaluate flow-volume loops and distinguish poor effort and restrictive lung diseases from asthma-related obstruction.²⁰⁻²² For all of these reasons, we feel it is pertinent to study this breath-enhanced nebulizer technology in relation to clinical spirometric data in order to demonstrate clinical efficacy.

VI. Research Method, Design, and Proposed Statistical Analysis

This study will be a blinded observer, randomized, controlled trial comparing breath-enhanced nebulizer albuterol therapy with nebulized albuterol administered via a t-piece nebulizer.

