
member of the study team (P2) will open the subject's randomized folder that will dictate the appropriate therapy arm. P2 will administer a single 5mg dose of albuterol via the appropriate nebulizer as determined by randomization. P1 will be blinded to the treatment arm, whereas P2 will not be blinded. Following 15 minutes of therapy - sufficient time for both treatment arms to be complete - P1 will perform a post-treatment assessment of the subject including a repeat set of vital signs, pulse-oximetry, asthma scoring, and spirometry measurements.

Patients randomized to the "control" arm will receive therapy with our standard ED nebulizer, the Hudson RCI® Micro Mist® nebulizer (Teleflex Medical®, Research Triangle Park, NJ). The treatment will be preferentially administered with a mouthpiece. Patients unable or unwilling to use a mouthpiece (as determined by the P2) will receive therapy with a simple mask (Hudson RCI®, Teleflex Medical®, Research Triangle Park, NJ).

Patients randomized to the "experimental" arm will receive therapy with a NebuTech® HDN®, Breath-Enhanced High Density Jet Nebulizer (Salter Labs®, Arvin, CA). Treatments will be preferentially administered with a mouthpiece. Patients unable or unwilling to use a mouthpiece (as determined by the P2) will receive therapy with a mask. The NebuTech® HDN® allows for a proprietary vented mask, which still utilizes the breath-enhanced features of the system (I-Guard™ Valved Aerosol Delivery System, Salter Labs®, Arvin, CA).

Spirometry measurements will be taken using a handheld spirometer which has been validated in healthy controls (NDD EasyOne®).²⁶ In keeping with the most recent American Thoracic Society guidelines, participants will be asked to perform a minimum of 3 and maximum of 8 forced expiratory maneuvers in order to obtain 3 adequate samples as determined by the device.²⁷ Based on prior data, more than 8 attempts at spirometry may result in patient fatigue which will artificially decrease the patient's performance on lung function testing²⁷. The highest recorded FEV₁ will be used for analysis. Flow-volume loops will be evaluated by a pulmonologist in order to assess adequacy of spirometry measurements for all patients, and those with inadequate loops will be excluded from FEV₁ analysis. The pulmonologist involved will be blinded to therapy arm.

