Potential subjects and their parent or guardian will have the nature of the research study as well as potential risks and benefits of enrollment explained by study personnel. Consent will be obtained from the parent or guardian of all subjects, and assent obtained from subjects who are at least 7 years of age. A consent form written in English or Spanish will be provided to the parent/guardian based on their preferred language. A Spanish interpreter will be utilized as needed to answer questions and ensure clear understanding of expectations after enrollment. Subjects and parents will be given adequate time to consider enrollment, and questions will be encouraged and answered prior to enrollment.

d. Research Protocol

It will be explained to subjects and guardians that if enrolled in the study, that study participation will involve receiving an albuterol therapy with either the control or experimental nebulizer, assigned randomly, and performing follow-up spirometry testing after treatment. It will be explained that all of these therapies will occur within the DCMC ED, and will take approximately 20 minutes from start to finish. Subjects will be informed that if medically necessary, other treatments will be given, and that following participation, that standard of care treatment for their condition will be performed. A detailed description of the research protocol is provided in section VI above.

e. Timeline

This study is expected to begin enrollment in July 2015 and run through June 2017, though target dates may need to be adjusted based on ongoing analysis of enrollment rate, as well as the percentage of patients able to successfully provide spirometry data. Data cleaning and analysis will be completed by August 2017. The target abstract completion data is November

2017, followed by manuscript writing and submission. DCMC ED sees approximately 3000 visits for asthma annually. With research staff available at a minimum of 18 hours per day, we expect to have no issue achieving adequate enrollment for this study within a two-year period.

f. Privacy and Confidentiality of Participants

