There is a potential risk to patients of loss of confidentiality. This risk is minimized utilizing the methods described above. If the experimental nebulizer shows decreased efficacy compared to the control arm, subjects may experience less bronchodilation, and subsequently may require more subsequent doses of albuterol, or other adjunctive therapies. There is no reason to believe that patients in the experimental group will experience greater discomfort than those patients in the control group.

Data and safety Monitoring:

This study involves 2 FDA approved nebulizers that have been used clinically for decades. The medication doses are similar to those used by children in the home setting. For these

reasons this study is considered very low risk and equivalent to the ED standard of care for non-study patients. Despite this, a Data and Safety Monitoring Plan will be in place for ongoing evaluation of the safety of this study. The DSMP will consist of the PI ([name]) and the Co-I ([name]) reviewing any reported adverse events within 24 hours of occurrence. Additionally, at the midpoint of the study (subject #107), there will be a scheduled interim analysis. During this analysis we will analyze group difference with regards to adverse event and admission rates. If, during either of these reviews, new information is discovered that would change the risk profile of the study, enrollment will be suspended and the IRB will be notified to help determine a course of action.

IX. Potential Benefits

The potential benefit of this trial is the possibility of a better understanding of the effect of breath-enhanced nebulizer technology on the treatment of acute asthma. Additionally, if we are able to demonstrate significant benefit of this new technology, this may enhance the treatment of future pediatric patients with asthma, at home or in the emergency department. The potential benefit of this study to the individual study patient is largely unknown. Patients who are randomized to the experimental arm of the study may experience greater bronchodilation due to improved medication delivery; however, this benefit is likely minimal given that this study is evaluating only a single dose of albuterol.

X. Sites or Agencies involved in the research project

Research activities will be carried out exclusively at Dell Children's Medical Center.

XI. Review by another IRB

Not applicable.

XII. Citations

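### Families hear the devices called control and experimental, neither child nor guardian is blinded, and the child then performs the effort-dependent test that gives the primary outcome

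*Combined protocol and SAP*

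**What the plan says.** Section VII.d says families will be told that participation involves "receiving an albuterol therapy with either the control or experimental nebulizer, assigned randomly, and performing follow-up spirometry testing after treatment". Section VII.c adds that subjects and guardians "will have the nature of the research study as well as potential risks and benefits of enrollment explained by study personnel".

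The text on benefit and risk points both ways. Section IX says patients "randomized to the experimental arm of the study may experience greater bronchodilation due to improved medication delivery; however, this benefit is likely minimal", and just before that it describes the benefit to the individual child as largely unknown. Section VIII gives the opposite possibility: "If the experimental nebulizer shows decreased efficacy compared to the control arm, subjects may experience less bronchodilation".

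Section VI calls the design blinded-observer. It states that "P1 will be blinded to the treatment arm, whereas P2 will not be blinded", and it also blinds the pulmonologist who reads the flow-volume loops. The child and guardian are not mentioned. The two nebulizers are different named products, and the control device is the one the ED normally uses. After the post-treatment assessment, only the blinded assessor (P1) is asked to guess the arm.

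On spirometry, section VI asks for 3 to 8 manoeuvres to obtain 3 that the device accepts. The highest FEV₁ is analysed, and children with inadequate loops are left out of the FEV₁ analysis. Screening spirometry is done before consent. Section V prefers FEV₁ to peak flow partly because loops make it possible to "distinguish poor effort and restrictive lung diseases from asthma-related obstruction".

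**The concern.** The trial wants to attribute a difference in FEV₁ change to drug delivery. A child who knows that the device in use is the experimental one, or is plainly not the usual one, may try harder or less hard at the second test. The guardian may also encourage the child differently. P1's blinding controls the observer but does not control the child's effort.

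If effort differs by arm, the difference is added to the device effect and cannot be separated from it afterwards. A larger sample does not help, because the bias stays the same while the standard error shrinks. The regression planned at the end of the Statistical Analysis section adjusts for baseline differences, and this effect would arise after baseline. Because only P1's guess is recorded, the data would not show what families believed.

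**Working it through.** **1. Can expectation reach the primary outcome?**

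- Labels: section VII.d gives non-neutral names as part of the planned explanation.
- Knowledge of the arm: no masking or sham is described. That the child can tell the devices apart is an inference from two facts in section VI. They are different products, and a child whose consent is delayed may already have used a standard t-piece up to three times.
- Timing: screening spirometry precedes consent. Children treated during a consent delay must still meet the entry criteria afterwards, which is also before randomization. Knowledge of the arm can therefore affect only the post-treatment value, and any effect passes in full into the between-arm difference in change.
- Safeguards: blinding P1 keeps the coaching even. Taking the highest value limits the harm from one poor blow. Device criteria and blinded loop review remove inadequate manoeuvres. None of these makes effort equal between arms among the loops that are accepted.

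**2. The plan's own sample size**

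Inputs from the Sample Size and Statistical Analysis sections: difference 5 points, power 0.80, two-sided alpha 0.05, t-test, 64 per arm. No SD is given, so 64 cannot be reproduced from the stated inputs alone and the SD must be back-solved.

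- Normal approximation at SD 10: n = 2 × (1.96 + 0.84)² × (10/5)² ≈ 62.8, so 63 per arm.
- Exact t-test at SD 10: 64 per arm, power 0.80.
- SDs for which the t-test gives exactly 64: about 9.94 to 10.02.

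The implied SD is therefore about 10 points.

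**3. Illustration of scale**

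The documents give no size for an expectation effect, so the values of b below are assumptions.

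SE of the difference = 10 × √(2/64) = 1.77 points.

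With no true device difference and an expectation effect b, the two-sided rejection rate is approximately

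1 − Φ(1.96 − b/SE) + Φ(−1.96 − b/SE).

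| Assumed b (points) | b/SE | Rejection rate | b as share of 5 |
|---|---|---|---|
| 0 | 0 | 5% | 0% |
| 0.5 | 0.28 | 5.9% | 10% |
| 1 | 0.57 | 8.7% | 20% |
| 2 | 1.13 | about 20% | 40% |

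At b = 1 the rate is 10.9% if the SD is 8 and 7.6% if it is 12. At b = 2 it is 29% and 16%. The two-sided rate is the same if b favours the control arm. In that case a true advantage of the breath-enhanced device would be understated by b.

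**The case against.** A reader might infer more than this: that families are told the experimental device may work better, and that the bias runs towards the trial's hypothesis. The documents do not support either step. VII.d summarises what will be explained and is not a script, and the consent wording is not available. Section IX gives possible greater bronchodilation but in the same sentence calls the benefit likely minimal, and section VIII lists lower efficacy as a possibility. If families hear risks and benefits as VII.c says, they hear both sides. A bias towards the hypothesis would also require that the child knows which device is experimental, believes it is better, and changes effort accordingly. None of this is shown.

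Two further objections have weight. The sentence on effort in section V presents loop review as a safeguard and does not concede that FEV₁ will be spurious. And the arithmetic shows only what a bias of a given size would do; it is not evidence that one exists.

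It can also be said that the plan is open about being blinded-observer only, and that neutral names will often be seen through because one device is the ED's usual one. That is true, and it limits what the change can achieve. It does not answer the point that non-neutral names, an unblinded child and an effort-dependent endpoint occur together, when one of the three can be changed at almost no cost.

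**Conclusion.** The point holds as a plausible, partly controlled route for bias into the primary outcome. The names used with families are documented. The child's unblinded status is inferred from the plan's silence and from the different devices. The existing safeguards are real and reduce the risk, but they do not equalise effort among accepted loops.

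Direction and size are unknown. The 8.7% figure for a 1-point effect rests on an assumed effect, a back-solved SD of about 10 and 64 analysable children per arm, and it serves only to show scale against a 5-point target. The change is worth making because it is cheap and agrees with the protocol's own position that both devices are FDA approved and that individual benefit is largely unknown.

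**What to change.** - In section VII.d, and in what is said at consent, at assent and at the bedside, use neutral names such as nebulizer A and nebulizer B. Say that both are FDA approved and that it is not known which works better.
- Instruct P2 not to describe either device as newer or better before the post-treatment spirometry.
- State in section VI that children and guardians are not blinded.
- Optionally, record which device the family believed was better. P2 should do this, or P1 only after entering P1's own guess, so that the blinding check is not contaminated.

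The cost is a minor IRB wording amendment, with no extra patients and at most one added question. Protection is partial, since some families will recognise the standard ED device. Section VII.e planned enrollment through June 2017. If enrollment has closed, what remains is to report that participants were not blinded and to list this as a limitation.
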